2.6. SCHEDULE OF TIME AND EVENTS

[figure not shown]
Each patient is uniquely identified by a Subject Number which is composed by the site number assigned by Novartis and a sequential number assigned by the investigator. Once assigned to a patient, the Subject Number will not be reused. Upon signing the informed consent form, the patient is assigned the next sequential number by the investigator.

The patient is followed up to Day 30 and relevant information is entered into the eCRF.

Table 2.6-1 lists all of the assessments and indicates with an "x" when the visits are to be performed.

Patients shall be seen daily through index hospitalization until Day 5, until discharge (whichever occurs first), and then at Day 14. If for any good reason, the assessments at Day 5 cannot be done on the designated day, a window of + 1 day is allowed. A "visit window" of +/- 2 days is allowed for Day 14 and for phone contact on Day 30.

Patients should be seen for all visits on the designated day or timepoint, or as close to it as possible. Patients are expected to return to the clinic for all scheduled study visits. Patients unable or unwilling to return to the hospital/clinic for scheduled visits will be contacted by telephone as close as possible to the expected visit to obtain information about survival status.

Statistical Analysis Plan

Sponsor: NOVARTIS

Protocol number: CRLX030A3301

Patients who prematurely discontinue the investigational treatment will remain in the study and shall undergo all the assessments illustrated in Table 2.6-1. If a patient withdraws from participation in the study, or refuses to return for study assessments, or is unable to do so, every effort shall be made to contact them or a knowledgeable informant by telephone and/or other measures to determine the patient's survival status during the follow-up period.

	Statistical Analysis Plan											
	Sponsor: NOVARTIS Protocol number: CRLX030A3301											

Table 2.6-1: Assessment schedule

Visit number	0	0-1	1-1	1-2	1-3	1-4	1-5	1-6	2		3	4
Time of Visit	Screening	End of Screening/ Baseline	6h	12h	24h	48h	D3	D4	D5 ¹²	Discharge ¹³	D14 (± 2)	D30 (± 2)
Phase			Drug Infusion⁰						Post-treatment daily assessment			Follow-up
Obtain Informed Consent	X											
Demographic data	X											
Inclusion/Exclusion criteria	X											
Medical history, including diagnostic of AHF, Alcohol, drug abuse, education level, living arrangement and smoking histories	X											

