Persistent signs and symptoms of HF/non-improvement

The number of patients with persistent symptoms or signs of HF / not showing an improvement versus baseline conditions through Day 5 (persisting need of IV therapy for HF) will be evaluated.

Patients with persistent symptoms or signs of HF / not showing an improvement versus baseline conditions through Day 5 are those patients who take any IV therapy for HF at each assessment time point as reported in the eCRF sections “IV Loop Diuretic Medication for Heart Failure” and “IV Medications Other than Loop Diuretics”.

Moreover, the investigator or appropriate qualified designee evaluates the symptoms and signs of heart failure, including dyspnea on exertion or at rest, orthopnea, rales, jugular venous pulse (JVP) and peripheral edema. These evaluations are performed at baseline, 6, 12, 24 and 48 hours from start of study drug infusion, daily through index hospitalization, at Day 5, at discharge and then at Day 14 for the serelaxin arm. For patients in the SOC arm, relevant evaluations are performed at baseline, at 6, 12, 24 and 48 hours from randomization, daily through index hospitalization, at Day 5, at discharge, and then at Day 14.

These evaluations should be done at approximately the same time of the day, each day, in the same position and hospital/clinic setting, preferably by the same assessor.

Renal deterioration

Renal deterioration is defined as an increase of ≥ 0.3 mg/dL from screening in serum creatinine levels. Rate of renal deterioration at 24 hours, at 48 hours, at Day 5, at discharge, and at Day 14 post randomization will be evaluated.

Serum creatinine evaluations are performed locally at screening, at 24 and 48 hours, at Day 5, at discharge, and then at Day 14 post randomization.

Index length of hospital stay

Index length of hospital stay (in hours) is defined as the index hospitalization discharge date and time minus the index hospitalization admission date and time + 1 minute.

Index length of hospital stay, from admission to discharge, will be evaluated by location (emergency ward, emergency care unit, etc.).

Index hospitalization details are collected in eCRF at Screening, Day 5, discharge visit, Day 14 and Day 30 post randomization.

	Statistical Analysis Plan
	Sponsor: NOVARTIS Protocol number: CRLX030A3301

Death through Day 30

All deaths (adjudicated or not) occurring from randomization through Day 30 will be used in the analysis.

Re-hospitalization post-discharge

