5. STATISTICAL METHODOLOGY

5.1. GENERAL METHODOLOGY

Data will be analysed according to the data analysis Section 9 of the study protocol.

All statistical tables, listings, figures and analyses will be produced using SAS® release 9.4 (64-bit) or later (SAS Institute Inc., Cary NC, USA).

The data from all countries and all sites will be pooled and summarized. Continuous data will be summarized by the mean, standard deviation (SD), median, first and third quartiles,

	Statistical Analysis Plan
	Sponsor: NOVARTIS Protocol number: CRLX030A3301

minimum and maximum. Categorical data will be presented by absolute and relative frequencies (n and %) or contingency tables.

All nominal time points will be used for analysis; actual assessment times will not be used to reclassify the time point at which a measure was taken. Time-to-event analyses will be based on actual dates (times) reported.

Subjects will be included in each efficacy analysis based on available assessments, after the data handling conventions have been applied. The prevalence approach (i.e., no imputation of missing data), if not differently indicated, will be applied.

Unless stated otherwise, two-sided p-values < 0.05 will be considered statistically significant. No formal interim efficacy analysis will be performed and therefore no statistical adjustment of alpha level will be required.

Visit, baseline and post baseline definitions

Screening phase: The screening phase is defined as the period prior to randomization. After obtaining written informed consent, the subject will be evaluated for eligibility to participate in the study.

Baseline definition for efficacy and safety measurements: Baseline date and time is defined as the date and time of initiation of study drug for the serelaxin group, or date and time of randomization for the SOC group. Of note, the randomization date and time will be used as the reference date and time for all time to event analysis.

Post-baseline phase for efficacy and safety measurements: The post-baseline phase begins at the date and time of initiation of study drug administration for the serelaxin group, or the date and time of randomization for the SOC group, and ends with the last study assessment/last follow-up or the death of subject. For subjects who did not receive study drug, the phase begins at the time of randomization.

Patient disposition and analysis population

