Absolute frequencies and proportions of patients with persistent symptoms or signs of HF / not showing an improvement at any visit vs. baseline (persisting need of IV therapy for HF) in each treatment group will be provided, and also at each assessment time point (24 hours, 48 hours, Day 3, Day 4) through Day 5 and at discharge, together with standard errors, asymptotic (Wald) and exact (Clopper-Pearson) confidence limits. The rates in the two groups will be compared by means of Chi square test at each time point. In case of cell frequencies less than 5, Fisher’s Exact test will be used.

Patients with persistent symptoms or signs of HF / not showing an improvement versus baseline conditions at each assessment time point are those patients who take any IV therapy for HF at the assessment time point as reported in the eCRF sections “IV Loop Diuretic Medication for Heart Failure” and “IV Medications Other than Loop Diuretics”.

Improvement in signs or symptoms of HF

A time-to-event analysis through Day 14 will be performed. Hazard ratios of being a responder for each of the signs and symptoms variables (response is defined as ≥ 1 point improvement from baseline) will be estimated using a Cox regression model with treatment as a factor.

Treatment groups will be compared with a Gehan’s generalized Wilcoxon test. The Kaplan-Meier estimates of the cumulative event rate will also be presented by treatment group.

One or more point improvement will be defined as a reduction from baseline of at least one point in the specific sign/symptom according to the score defined in the table below.

Statistical Analysis Plan

Sponsor: NOVARTIS

Protocol number: CRLX030A3301

Table 5.2-5: Scores for the definition of improvement

	Categorical value	Numerical value
Dyspnea on exertion	None	0
	Mild	1
	Moderate	2
	Severe (including dyspnea at rest)	3
Orthopnea	None	0
	1 pillow (10cm)	1
	2 pillows (20cm)	2
	>30 degrees	3
Edema	0	0
	1+	1
	2+	2
	3+	3
Rales	No rales	0
	Rales <1/3	1
	Rales 1/3-2/3	2
	Rales >2/3	3
Jugular venous pulse (JVP)	<6cm	0
	6-10cm	1
	>10cm	2
Body weight increase	No	0
	Yes	1

The scores will be presented as both categorical and continuous (i.e., numerical values in Table 5.2-5) statistics. Change from baseline will be computed as the baseline value subtracted from the post baseline values. Cross tabulation of categorical values at baseline and at each assessment time point will be presented by treatment group.

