Each sign or symptom of HF, collected in “Physician Assessment of Signs and Symptoms of Heart Failure” eCRF page, will be analysed separately. The event is defined as ≥ 1 point improvement from baseline. The time to being a responder will be computed as the number of hours from randomization to the date and time of the first assessment at which a ≥ 1 point improvement from baseline is detected plus 1 minute. Subjects without an event will be censored at the earlier of the last post-baseline assessment of signs and symptoms of HF or 336 hours (i.e., 14 days) after randomization. Subjects without any information after baseline (i.e., randomization) will be considered censored at 1 minute. In case of missing time of assessment of signs and symptoms of heart failure then 00:00 will be imputed. The analysis will be performed excluding subjects with the following signs and symptoms at baseline: ‘None’ for Dyspnea on exertion and Orthopnea; ‘0’ for Edema; ‘No rales’ for Rales; ‘<6 cm’ or ‘Not evaluable’ for Jugular venous pulse, ‘No’ for Body weight increase.

Table 5.2-6: Censoring and time rules

	Statistical Analysis Plan
	Sponsor: NOVARTIS
	Protocol number: CRLX030A3301

	Status	Time
At least one (≥ 1) point improvement occurred and:		
Difference between date and time of first occurrence improvement (i.e., date and time of physician assessment where improvement was assessed) and date and time of randomization +1 minute > 336 hours	Censored	336h
Difference between date and time of first occurrence improvement (i.e., date and time of physician assessment where improvement was assessed) and date and time of randomization +1 minute ≤ 336 hours	Event	Calculated difference
No improvement occurred and		
Difference between date and time of last available physician assessment and date and time of randomization +1 minute > 336 hours	Censored	336h
Difference between date and time of last available physician assessment and date and time of randomization +1 minute ≤ 336 hours	Censored	Calculated difference

Moreover, summary statistics for data about physician assessment of signs and symptoms of HF will be provided at each assessment time point by treatment group. Absolute and relative frequencies of patients reporting each sign/symptom will be provided. Percentages will be computed considering patients with non-missing information at each assessment time point and by each type of sign and symptom.

Renal deterioration

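### The sign-and-symptom responder analysis dates improvement at the detecting visit, but the 6 to 48 h visits run on a later clock on serelaxin, which biases the Gehan test and Cox hazard ratio against serelaxin when early visits are kept close to schedule

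*SAP*

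**What the plan says.** SAP section 5.2, under improvement in signs or symptoms of HF, analyses each sign separately through Day 14. The event is a reduction of at least one point from baseline. Its time is defined in the text above Table 5.2-6: "The time to being a responder will be computed as the number of hours from randomization to the date and time of the first assessment" that detects the improvement, plus one minute, censored at 336 h. Section 5.1 confirms the origin, "the randomization date and time will be used as the reference date and time for all time to event analysis", and the use of actual times: "Time-to-event analyses will be based on actual dates (times) reported". The arms are compared with Gehan's generalized Wilcoxon test, and the hazard ratio of response "will be estimated using a Cox regression model with treatment as a factor".

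The visits are scheduled differently by arm. For serelaxin, SAP section 4.1 says: "These evaluations are performed at baseline, 6, 12, 24 and 48 hours from start of study drug infusion, daily through index hospitalization". For the comparator it says: "For patients in the SOC arm, relevant evaluations are performed at baseline, at 6, 12, 24 and 48 hours from randomization". Protocol section 6.4.1.1 has the same split.

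Protocol section 5.5.5 puts the gap between randomization and infusion start at 30 to 60 minutes in most cases and states that no time window is mandatory.

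On visit precision, SAP section 2.6 gives no hour window for the early visits: "Patients should be seen for all visits on the designated day or timepoint, or as close to it as possible". Section 4.1 adds a competing instruction: "These evaluations should be done at approximately the same time of the day, each day, in the same position".

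**The concern.** Improvement can be recorded only when someone looks. On serelaxin the first four looks come later after randomization, by the time it takes to start the infusion, while the analysis clock starts at randomization in both arms. Patients who improve at the same rate then get systematically later response times on serelaxin. Both planned methods read that as slower improvement. Gehan's test is hit harder than Cox because it gives most weight to the earliest visits.

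At stake is a set of two-sided 0.05 comparisons, one per sign, with no multiplicity adjustment. The same offset acts on every sign assessed at the early visits, so several false results in the same direction could look like corroboration. A real benefit could be diluted or hidden. The primary endpoint is not reached by this route, because it uses the reported start date and time of the event.

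**Working it through.** The documents give no figure for this analysis, so there is none to reproduce. The check is an exact illustration followed by simulation.

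**Inputs from the documents.** 3183 patients randomized 2:1; visits at 6, 12, 24 and 48 h on the two clocks above, then Days 3, 4, 5 and 14; censoring at 336 h; delay to infusion of 0.5 to 1.0 h; two-sided alpha 0.05.

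**Assumptions.** Speed of improvement and visit scatter. Neither is in the documents, so both are varied.

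**Step 1: exact illustration, no drug effect.** Assume 25% improved by 6 h and 70% by 48 h on a Weibull curve, F(t) = 1 − 0.75^((t/6)^k). Then k = ln[ln 0.30 / ln 0.75] / ln 8 = 0.688. Visits are kept exactly and the serelaxin delay is 0.75 h.

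| Visit | F, SOC | F, serelaxin | First seen, SOC | First seen, serelaxin | Product |
|---|---|---|---|---|---|
| 6 h | 0.250 | 0.268 | 0.250 | 0.268 | 0.0670 |
| 12 h | 0.371 | 0.383 | 0.121 | 0.115 | 0.0139 |
| 24 h | 0.526 | 0.534 | 0.155 | 0.150 | 0.0234 |
| 48 h | 0.700 | 0.704 | 0.174 | 0.170 | 0.0295 |

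The products sum to 0.134. In 13.4% of serelaxin–SOC pairs both patients respond at the same early visit, and every such pair is ranked SOC first. The later look catches slightly more improvement on serelaxin, worth 1.4% of pairs over all visits. The net Gehan contrast is 0.014 − 0.134 = −0.120, where it should be zero.

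**Step 2: simulated null.** The delay is uniform on 0.5 to 1.0 h. The curves have 10%, 20% or 30% improved by 6 h (slow, middle, fast), identical in both arms. Scatter is Gaussian at the 6 to 48 h visits; later visits share one clock. There were 2000 datasets per cell with 2122 and 1061 patients. With no offset the Gehan test rejected in 5.3%, 4.3% and 5.6%, with hazard ratio 1.00. With the offset (two-sided rejection, slow/middle/fast):

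| Scatter SD | Gehan, all four visits offset | Gehan, only 6 and 12 h offset | Mean response HR, all four offset |
|---|---|---|---|
| 0.25 h | 47/97/100% | – | – |
| 0.5 h | 27/80/99% | 7/31/86% | 0.97/0.95/0.92 |
| 1 h | 11/26/55% | 6/10/28% | 0.99/0.98/0.96 |
| 2 h | 5/7/11% | 5–6% | – |
| 3 h | 5/7/7% | 5–6% | – |

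At SD 1 h or less nearly all rejections go against serelaxin. Cox Wald rejection with all four visits offset is 10/28/59% at 0.5 h and 6/10/17% at 1 h. If patients without the sign at baseline cut N to 1910 (an assumption), Gehan rejects in 17/56/92% at 0.5 h and 9/16/37% at 1 h.

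**Step 3: different assumptions.** With Weibull curves, uniform scatter of ±1 h and no drug effect, the result was significant against serelaxin in 9% of trials for 3%/25% improved by 6/48 h (HR 0.988), 34–39% for 10%/50% (HR 0.97) and 88–89% for 25%/70% (HR 0.944). The nominal rate in that direction is 2.5%. At ±4 h the hazard ratios for 10%/50% and 25%/70% were 0.991 and 0.990.

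**Step 4: a real benefit.** With a true response hazard ratio of 1.2 and all four visits offset, Gehan finds the benefit in 70/17/1% at SD 0.5 h and 90/76/43% at 1 h. An interval-censored Wilcoxon test finds it in 97–99%.

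**The case against.** Nobody disputes the two clocks. The strongest objection is that the size rests on two quantities the documents do not give. Over the scatter and curves tried, Gehan rejection runs from 5% to 100%. If ward practice spreads the early visits by 2 to 3 h, little bias remains. That stands. But the SAP asks for visits as close to schedule as possible, so the better the sites comply, the larger the bias.

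The same-time-of-day instruction may also put the 24 and 48 h visits on ward rounds in both arms. That too is fair, and the middle column of the Step 2 table then applies: slow signs are barely affected. The 6 and 12 h visits cannot follow a daily-time rule, and fast-improving signs stay biased.

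Third, this is a secondary, unadjusted analysis, the error runs against the experimental drug, and the SAP already tabulates each sign by visit and arm, so a reader could see that the proportions improved do not differ. This limits the harm. It does not justify a two-sided test that can report significantly slower improvement under no effect.

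Two smaller points also stand. Excluding patients without the sign at baseline lowers N for most signs. Body weight is not scheduled at 6 or 12 h, so that item may escape the early offset.

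**Conclusion.** The concern holds: as written, the responder time builds a between-arm difference in assessment schedule into the outcome, and no rule in the SAP removes it. The mechanism and its direction follow from the text. The size is conditional. With early visits within about 1 h of schedule, the bias is large for signs that often improve by 6 to 12 h and modest for slow ones. At scatter of 2 to 3 h it is near nominal, and it is small for slow signs if only the 6 and 12 h visits are offset. These results assume a delay of 0.5 to 1.0 h. With 25%/70% improved and ±1 h scatter, a delay of 0.25 to 0.5 h gives HR 0.969 and a delay of 1 to 2 h gives 0.918. No scenario run under the planned analysis produced a false benefit for serelaxin. The point should be fixed before unblinding, but it does not touch the primary conclusion.

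**What to change.** Treat the responder time as interval-censored on the randomization clock. The event lies after the last assessment without, and no later than the first assessment with, at least a one-point improvement. Non-responders are right-censored at their last assessment, at most 336 h. Compare the arms with an interval-censored generalized Wilcoxon test and estimate the hazard ratio with an interval-censored proportional-hazards model, in place of the Gehan test and the Cox model on raw assessment times. Where an assessment time is missing, bound it by the calendar day instead of setting it to 00:00. Protocol section 9.5.1 names a Cox model for these hazard ratios, so the SAP should record the change.

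Do not switch to nominal visit times. Each nominal visit falls later after randomization on serelaxin, and under the Step 3 assumptions (±1 h scatter) this gave null hazard ratios of 1.001 to 1.016, a small bias towards serelaxin.

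In simulation the interval-censored test rejected in 3.7% to 5.7% of null trials at scatter SD 0.5 h or more (600 datasets per cell). The interval-censored hazard ratio averaged 0.99 to 1.01, though on only 60 datasets per cell. At SD 0.25 h the arms' visit times barely overlap and the test ran at 6% to 8%, a residual limit worth stating. The cost is SAP wording and somewhat more programming; the assessment dates and times are already collected.

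### The exact 336-hour cut in the time-to-improvement analysis censors first improvements found at late but in-window Day 14 visits

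*SAP*

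**What the plan says.** SAP 5.2, under Improvement in signs or symptoms of HF, analyses each sign or symptom separately: "A time-to-event analysis through Day 14 will be performed". The event is a drop of one point or more: "One or more point improvement will be defined as a reduction from baseline of at least one point in the specific sign/symptom". Its time is "computed as the number of hours from randomization to the date and time of the first assessment" at which the improvement is seen, plus 1 minute. Patients without an event are censored at the "earlier of the last post-baseline assessment of signs and symptoms of HF or 336 hours (i.e., 14 days) after randomization". Table 5.2-6 adds that a first improvement assessed more than 336 h after randomization has status Censored and time 336 h. Its last row censors a patient who is not improved, and whose last assessment falls by 336 h, at the time of that assessment. The planned outputs are a Cox hazard ratio, a Gehan test and Kaplan-Meier cumulative rates by arm.

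On visit timing, SAP 2.6 states that a window "of +/- 2 days is allowed for Day 14 and for phone contact on Day 30". Section 6 of the protocol says the same.

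SAP 5.1 sets two rules for clock time. For nominal time points, "actual assessment times will not be used to reclassify the time point at which a measure was taken". For the analysis at issue, "Time-to-event analyses will be based on actual dates (times) reported". The origin is common to both arms: "the randomization date and time will be used as the reference date and time for all time to event analysis". No window exception is given for the improvement analysis.

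**The concern.** A fixed limit in hours suits events that carry their own time. Worsening heart failure is dated at its reported start, and death and readmission have their own dates. Improvement has no onset time here, only the time of the visit that detects it. After discharge, the next scheduled assessment is Day 5 (if not yet reached) or Day 14. For a discharged patient still unimproved, the Day 14 visit is therefore the only late chance to record a response.

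Under Table 5.2-6 that response is an event if the visit falls at 335 h and a censored observation if it falls at 338 h. Both visits comply with the schedule. What is at stake is the Kaplan-Meier response rate at Day 14. It would also disagree with the SAP's own nominal tables: a patient seen on Day 15 and improved counts as improved in the Day 14 cross-tabulation, but has no event by Day 14 in the survival analysis.

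**Working it through.** **1. The plan's own figure.** 14 x 24 = 336 h, as stated. Protocol 3.1 equates 48 hours with Day 2, so Day n is n x 24 h. The Day 14 window therefore runs from about 12 x 24 = 288 h to 16 x 24 = 384 h.

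**2. Same-day example.** A patient randomized at 08:00 and seen at 10:00 on Day 14 is at 338 h, so a first improvement found then is censored.

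**3. Share of Day 14 visits after 336 h.** The documents give no visit-time distribution, so it is assumed. Clinic hours are taken as 08:00-17:00 (mean 12.5). If all visits are on Day 14 and the hour of randomization is uniform, the share is 12.5/24 = 52%. Simulated shares (1,000,000 draws) are below. The first column has the randomization hour uniform over 24 h; the second has it centred on 15:00 with SD 4 h.

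| Visit days | Uniform | Afternoon |
|---|---|---|
| All on Day 14 | 52% | 30% |
| Triangular around Day 14 | 51% | 44% |
| Even over Days 12-16 | 50% | 46% |
| Skewed early (30/30/30/5/5%) | 26% | 19% |
| Skewed late (5/5/30/30/30%) | 76% | 69% |

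Visits all on Days 12-13 give 0%, and all on Days 15-16 give 100%. If the randomization date were Day 1, the even case with uniform hour would give 30%.

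**4. Effect on the Kaplan-Meier rate at 336 h.** Let q be the share of patients unimproved before the Day 14 visit, r the share of these improved at it, and s the share of visits after 336 h. Assume no dropout and that improvement does not depend on visit timing. Patients seen by 336 h leave the risk set at their visit, as events (r) or censored (1 - r). The Kaplan-Meier response at 336 h in this group is then 1 - s^r, against r at the nominal visit. The shortfall over all patients is q x (s^r - (1 - r)). Take q = 5-20% and r = 50-70%; both are assumptions.

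- Symmetric visits, s = 0.5:
  - r = 0.5: 1 - 0.5^0.5 = 29% instead of 50%; the low end is 0.05 x 0.207 = 1.0 point.
  - r = 0.7: 1 - 0.5^0.7 = 38% instead of 70%; the high end is 0.20 x 0.316 = 6.3 points.
- Late-skewed visits, s = 0.75:
  - r = 0.5: 0.866 - 0.5 = 0.366, or 1.8 to 7.3 points.
  - r = 0.7: 0.818 - 0.3 = 0.518, or 2.6 to 10.4 points.
- Early-skewed visits, s = 0.2:
  - r = 0.5: 0.447 - 0.5 = -0.053, a slight overstatement of 0.3 to 1.1 points.
  - r = 0.7: 0.324 - 0.3 = 0.024, an understatement of 0.1 to 0.5 point.

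The sign can turn at the early end because the last row of Table 5.2-6 removes early-visit non-improvers from the risk set before 336 h.

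**5. Effect on the treatment comparison.** An illustrative Cox simulation used 2:1 allocation, an assumed hazard ratio of 1.2, the planned assessment grid and Day 14 visits even over Days 12-16 in both arms. Where 5.6% of first improvements were first seen at Day 14, 2.9% of all events were lost, and the estimated hazard ratio was 1.196 with the cut at 336 h against 1.192 with the cut at 384 h. Where the share was 15.4%, 8.4% of events were lost, and the ratios were 1.187 and 1.186.

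**The case against.** The best defence is that SAP 5.1 settles the matter: time-to-event analyses use actual times, and censoring at the horizon is the convention throughout 5.2. A finding first made at 380 h was not observed by 336 h. This stands as a reading of the text: the rule is clear and does not conflict with 5.1. It does not remove the problem, because the analysis is labelled through Day 14 while the rule drops findings from visits that the schedule counts as Day 14.

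Three stronger inferences are tempting, and the documents do not support them.

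- **About half of Day 14 improvements are recorded as non-response.** No visit timing is given, so one half is only the symmetric case. The status is Censored, although at the end of follow-up the effect is no event by Day 14.
- **The Day 14 data are lost for about half the patients.** Patients improved at 6, 12, 24 or 48 h, daily in hospital, at Day 5 or at discharge are unaffected. The nominal tables also keep every Day 14 result, including those of late visits.
- **The comparison of arms is biased.** The rule, the time origin and the window are the same in both arms, Gehan's test gives late events less weight, and the simulated hazard ratio hardly moves. The analysis is secondary, without multiplicity control, and the primary endpoint is dated at onset.

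**Conclusion.** The concern holds in a limited form. A first improvement found at a compliant Day 14 visit held after 336 h is censored instead of counted. The share of Day 14 visits affected is about half if they are symmetric around 336 h and plausibly 20-75%.

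With symmetric visits, and with the assumed 5-20% unimproved before the visit and 50-70% of these improved at it, the Kaplan-Meier Day 14 response is understated by about 1 to 6 percentage points per sign. The shortfall grows if visits run late, and it vanishes or slightly reverses if they run early. The rate therefore depends on visit logistics as well as on response.

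This is a defect in a reported secondary rate. It gives no reason to expect a material change in the hazard ratio or the Gehan test, and it leaves the primary analysis untouched.

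**What to change.** Amend two rows of Table 5.2-6 and the matching censoring sentence in SAP 5.2.

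1. Count an improvement first recorded at the nominal Day 14 visit, within its allowed window, as an event at the smaller of its actual time and 336 h.
2. Censor at 336 h every patient assessed as not improved at that in-window visit, including visits held before 336 h.

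Both rows must change. If only the late-improver row changes, early non-improvers still leave the risk set, and response is overstated. With symmetric visits and r = 50%, the estimate among patients reaching the visit unimproved becomes 1 - 0.5^0.5 x 0.5 = 65%. With r = 70% it becomes 1 - 0.5^0.7 x 0.3 = 82%. With both rows changed, nobody assessed at the visit is censored before 336 h, and the estimate returns r.

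State this as an exception to the actual-times rule in SAP 5.1. Protocol 9.5.1 sets no horizon for this analysis, so its text appears to need no change.

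The cost is two table rows, one sentence, the exception and the programming, with no new data. The small downside is that late visit times are capped at 336 h, and non-improvers seen early are carried forward to 336 h, beyond their last assessment.
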